Millennium	Millennium Pharmaceuticals, Inc., and its affiliates
MMAE	monomethyl auristatin E
mPFS	modified progression-free survival
MRI	magnetic resonance imaging
MRU	medical resource utilization
MTD	maximum tolerated dose
NCCN	National Comprehensive Cancer Network
NCI	National Cancer Institute
NCI CTCAE	National Cancer Institute Common Terminology Criteria for Adverse Events
NOAEL	no-observed-adverse-effect level
NYHA	New York Heart Association
ORR	objective response rate

OS	overall survival
PCR	polymerase chain reaction
PD	progressive disease (disease progression)
PET	positron emission tomography
PFS	progression-free survival
P-gp	P-glycoprotein
PK	pharmacokinetic(s)
PML	progressive multifocal leukoencephalopathy
PN	peripheral neuropathy
PR	partial response
PRO	patient-reported outcome
q3wk	every 3 weeks
QALY	quality-adjusted life year
QOL	quality of life
QTc	rate-corrected QT interval (millisec) of electrocardiograph
QTcF	Fridericia's corrected QT interval
RBC	red blood cell
SAE	serious adverse event
SCT	stem cell transplant
SD	stable disease
SJS	Stevens-Johnson syndrome
SmPC	Summary of Product Characteristics
SMQ	Standardised MedDRA query
SPD	sum of the product of the (tumor) diameters
$t_{1/2}$	terminal disposition half-life
Tab	total antibody
TARC	thymus- and activation-regulated chemokine
TGD	tumor growth delay
TGI	tumor growth inhibition
TK	toxicokinetics
TLS	tumor lysis syndrome
T_{\max}	single-dose first time of occurrence of maximum (peak) concentration
TNF-R	tumor necrosis factor-receptor
UK	United Kingdom
ULN	upper limit of the normal range

URTI	upper respiratory tract infection
US	United States
USAN	United States Adopted Name
USP	United States Pharmacopeia
Vss	steady state volume of distribution
WBC	white blood cell
WFI	water for injection
WHO	World Health Organization

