patients with relapsed or refractory sALCL, brentuximab vedotin was administered at a dose of 1.8 mg/kg every 3 weeks. One hundred two patients with relapsed and refractory HL and 58 patients with relapsed and refractory sALCL were exposed for a median duration of approximately 27 weeks (9 cycles) and 20 weeks (6 cycles), respectively. Most patients (89%) in the 2 phase 2 studies were between the ages of 18 and 65 years. The primary endpoint of both studies was overall response rate (ORR) as assessed by an independent review facility (IRF). Key secondary endpoints included duration of response, CR rate per IRF, OS, and progression free survival (PFS). The key efficacy results in HL (SG035-0003) include ORR per IRF (75% [95% confidence interval (CI): 64.9-82.6%]), CR rate per IRF (33% (34 of 102 patients in ITT set), B symptom resolution rate (77%), and duration of response (DOR; 6.7 months). After approximately 3 years of follow-up (median observation time from first dose = 32.7 months, range, 1.8 to 48.3 months), the median PFS was 5.6 months (95% CI: 5.0, 9.0 months [range, 1.2 to 44.4+ months]) and the median OS was 40.5 months (95% CI: 28.7, – months [range, 1.8 to 48.3+ mos]). The estimated 36-month survival rate was 54% (95% CI: 44%, 64%). Key efficacy endpoints in sALCL (SG035-0004) include ORR per IRF (88% [95% CI: 74.6-93.9%]), CR rate per IRF (59% (34 of 58 patients in ITT set), and B symptom resolution rate (82%). Patients have been followed for approximately 3 years (median observation time from first dose = 33.4 months, range, 0.8 to 45.6 months). The estimated 36-month survival rate was 63% (95% CI: 51%, 76%) and the median PFS was 14.6 months (95% CI: 6.9, 20.6 months [range, 0.8 to 40.4+ months]). The median OS has not yet been reached (95% CI: 21.3, – months [range, 0.8 to 45.6+ months]).

Summary of the safety profile

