2.2 Secondary Objectives

The key secondary objective is

To evaluate the safety profile of brentuximab vedotin using CTCAE version 4.03

Other secondary objectives include:

- To calculate progression-free survival (PFS) time
- To calculate the duration of response
- To calculate overall survival (OS) time

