7.1.6 Efficacy Analysis

All efficacy evaluations will be conducted using the ITT population unless otherwise specified. ORR will be used for the primary efficacy analysis using revised response criteria for malignant lymphoma (Appendix 12.3) or modified SWAT (Appendix 12.4) criteria. Duration of response in subjects with confirmed response is the time between first documentation of response and disease progression.

PFS and OS will be analyzed based on the ITT population using a stratified log-rank test. PFS is defined as the time from the date of randomization to the date of the first of (1) documentation of PD; (2) death due to any cause; (3) for patients who are confirmed non-complete responders, receipt of anticancer chemotherapy or radiotherapy for EBV- and CD30-positive lymphoma after completion of brentuximab vedotin. OS is defined as the time from the date of study enrollment to the date of death. Patients without documented death at the time of analysis will be censored at the date last known to be alive. Stratified log-rank testing will be used to compare OS between the groups. The hazard ratios along with the 95% CIs will be estimated using a stratified Cox regression model. The Kaplan-Meier method will be used to estimate the distribution of the OS endpoint. Median survival times (if estimable), along with the 2-sided 95% CIs will be presented. Analysis of OS will be performed based on the ITT population.

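### Section 7.1.6 counts new chemotherapy or radiotherapy without progression as a PFS event in non-complete responders only, and gives no rule for complete responders who receive it

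*Combined protocol and SAP*

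**What the plan says.** Section 7.1.6 opens the definition with "PFS is defined as the time from the date of randomization to the date of the first of (1) documentation of PD". Death from any cause is the second event. The third applies only to confirmed non-complete responders: "receipt of anticancer chemotherapy or radiotherapy for EBV- and CD30-positive lymphoma after completion of brentuximab vedotin".

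The section does not say what happens to a complete responder who starts new treatment without relapse. Its only censoring sentence is "Patients without documented death at the time of analysis will be censored at the date last known to be alive", which follows the definition of OS and serves that endpoint. Duration of response, in the same section, has no new-therapy component: "Duration of response in subjects with confirmed response is the time between first documentation of response and disease progression".

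The objective in Section 2.2 is "To calculate progression-free survival (PFS) time", and Section 3.2 lists the endpoint simply as PFS. Section 4.3 names PFS beside the response rate in the final analyses. Sections 4.1 and 7.1.2 confirm that nobody is randomized.

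**The concern.** PFS is normally time to progression or death. Here a third event is added for some patients and not others, and what separates them is response to the study drug, observed after treatment starts. Two patients with the same course of disease and the same later radiotherapy can then contribute different PFS times because one was classed as a complete and the other as a partial response.

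At stake is the meaning of a reported secondary endpoint. Part of any fall in the curve could reflect decisions to treat residual disease, not progression. Because no rule covers complete responders, the analyst must choose between following them on and censoring them, and that choice could be made after the data are seen. Duration of response and PFS would also treat the same treatment decision differently in the same patient.

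**Working it through.** **What can be reproduced.** The documents give no PFS median, event count or power. The only design figure is for the response rate (Section 7.1.1: p0 = 0.20, p1 = 0.45, rule 2/10 then 7/22). Exact binomial enumeration gives a type I error of 0.0492 and power of 0.8065, and 22/(1 − 0.10) = 24.4 rounds up to 25. That design reproduces and does not use PFS.

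**One course of disease under the written rules.** Assumed times: first response at 1.5 months, radiotherapy without progression at 5 months (after the last dose), progression or relapse at 12 months.

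- Partial responder: PFS is an event at 5 months. Duration of response is 12 − 1.5 = 10.5 months, longer than the same patient's progression-free time.
- Complete responder: the radiotherapy is not an event. If followed on, PFS is an event at 12 months. If censored at radiotherapy, it is a censored 5 months. The text does not choose.

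**Size per patient.** With 25 patients and nobody censored earlier, one extra event lowers the Kaplan-Meier curve by 1/25 = 0.04, or 4 percentage points. The gap from a progression-or-death curve closes when that patient would have progressed or died anyway. It is a ceiling at any later time point, not a permanent shift.

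**Illustration on assumed inputs, none of them in the documents.** Times to progression or death are exponential, with median 14 months in complete responders and 5 months in the others. The complete-response share is 15% or 30%. Between 10% and 30% of patients, whatever their response, are assigned new therapy uniformly between 2 and 6 months; it counts only if they are still progression-free. New therapy does not change the time to progression and is unrelated to prognosis within a response group.

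| CR share | Assigned new therapy | Progression or death: median (months), 6-month rate | Section 7.1.6 rule: median (months), 6-month rate | Non-CR patients treated without PD, of 25 | CR patients treated without relapse, of 25 |
|---|---|---|---|---|---|
| 15% | 10% | 5.7, 48% | 5.2, 44% | 1.2 | 0.3 |
| 15% | 20% | 5.7, 48% | 4.7, 41% | 2.5 | 0.6 |
| 15% | 30% | 5.7, 48% | 4.4, 37% | 3.7 | 0.9 |
| 30% | 10% | 6.5, 53% | 5.9, 50% | 1.0 | 0.6 |
| 30% | 20% | 6.5, 53% | 5.5, 47% | 2.0 | 1.2 |
| 30% | 30% | 6.5, 53% | 5.1, 44% | 3.0 | 1.9 |

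Under these assumptions the median falls by about 0.5 to 1.4 months and the six-month rate by about 3 to 11 points. The third row shows the ceiling at work: 3.7 × 4 = 14.8 points at most, against about 11 at six months, because some of those patients would have progressed by then anyway.

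**The case against.** The composite is stated openly, and counting new treatment as failure in patients with residual disease is a defensible, conservative choice: such patients may be treated because their response is inadequate, so censoring them could bias PFS upward. This stands as a caution about the remedy. It does not justify calling the composite PFS or leaving complete responders without a rule.

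Several stronger readings are tempting, but the documents do not support them:

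- A reader might infer an upward bias because complete responders keep accruing progression-free time after new treatment. The section is silent on PFS censoring, so this is possible but not established.
- A reader might infer that a non-complete responder who stops early is missed because treatment was not completed. Section 4.1 says patients may stop at any time and then times the end-of-treatment visit from completion of the last dose. Read that way, early stopping is covered; the word needs stating in 7.1.6, but no gap is shown.
- The abbreviation list contains "modified progression-free survival" as a separate entry. A reader might take this as the authors' own name for the composite. The list holds many terms the plan never uses, so the entry proves nothing.
- Section 1.4 reports "the median PFS was 5.6 months" in relapsed or refractory Hodgkin lymphoma. A reader might conclude that a planned comparison is spoiled. No PFS benchmark or external comparison is planned, and the documents do not say how that study handled new therapy.
- A reader might infer from the follow-up footnote to the schedule of events that new-therapy dates are collected only after progression. The sentence permits telephone contact in those patients; the one before it has all treated patients followed for PFS and OS.

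The clause also sits in a paragraph that starts PFS at randomization and compares groups in a non-randomized, single-treatment trial. That is fair, and one rewrite can deal with both.

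**Conclusion.** The point holds as a fault in the definition of a secondary endpoint. Section 7.1.6 makes new chemotherapy or radiotherapy without progression an event or a non-event according to response, and leaves its handling in complete responders unspecified. Nothing elsewhere in the documents corrects this.

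The established effect is downward relative to progression-or-death PFS: up to about 4 points per non-complete responder treated without progression, given 25 patients and no earlier censoring, and only until that patient would have failed anyway. How many such patients there will be is unknown, since the documents give no rate of post-study treatment without progression. The illustrated 3 to 11 points at six months and 0.5 to 1.4 months on the median depend entirely on the assumed inputs.

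The direction for complete responders cannot be stated. The response rate, the Simon rule and the move to stage 2 are not touched. The correction should be made, but it does not threaten the trial's main conclusion.

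**What to change.** Rewrite the PFS definition in Section 7.1.6:

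1. PFS runs from enrolment or first dose (choose one; there is no randomization) to progression, relapse or death from any cause. Relapse should be named because Appendix 12.3 uses a separate category for recurrence after complete remission.
2. State one rule for subsequent anti-lymphoma therapy for every patient, regardless of response or reason for stopping. For example, the main analysis follows patients through new therapy to progression, relapse or death, and a sensitivity analysis censors at the last adequate assessment before it. Censoring is better as the sensitivity analysis because it may be informative in partial-response and stable-disease patients.
3. State when a patient without an event is censored for PFS.
4. If the present composite is wanted, report it as a supportive endpoint labelled modified PFS, with completion of study drug stated as the last dose.

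The cost is wording in one section and one or two extra Kaplan-Meier tables, with no change to sample size. Neither handling of new therapy is free of bias: following through credits later treatment to the study drug, and censoring may remove patients who are doing badly. That is why both should be shown.

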7.1.7 Biomarkers

Baseline value of circulating biomarkers will be summarized by time point using descriptive statistics, as applicable. Descriptive statistics (eg, number of patients, mean, standard deviation, median, minimum, maximum) will also be provided to summarize the levels of soluble CD30 receptor and qualitative and semiquantitative measures of CD30 expression.

7.1.8 Safety Analysis

Safety will be evaluated by the incidence of AEs, severity and type of AEs, and by changes from baseline in the patient's vital signs, weight, and clinical laboratory results using the safety population. Exposure to frontline therapy and reasons for discontinuation will be tabulated.

Treatment-emergent AEs that occur after administration of the first dose of study drug and through 30 days after the last dose of brentuximab vedotin will be tabulated.

AEs will be tabulated according to the Medical Dictionary for Regulatory Activities (MedDRA) and will include the following categories:

- Treatment-emergent AEs
- Drug-related treatment-emergent AEs
- Grade 3 or higher treatment-emergent AEs
- Grade 3 or higher drug-related treatment-emergent AEs
- The most commonly reported treatment-emergent AEs (ie, those events reported by 10% of all patients)
- SAEs

All concomitant medications collected from screening through the study period will be classified to preferred terms according to the World Health Organization (WHO) drug dictionary.

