1.6 Potential Risks of brentuximab vedotin

As detailed in the Clinical Experience Section 1.4, brentuximab vedotin monotherapy has demonstrated therapeutic activity in CD30+ hematological malignancies.

Brentuximab vedotin treatment causes a peripheral neuropathy that is predominantly sensory. Cases of peripheral motor neuropathy have also been reported. Monitoring patients for symptoms of neuropathy, such as hypoesthesia, hyperesthesia, paresthesia, discomfort, a burning sensation, neuropathic pain or weakness is required. Patients experiencing new or worsening peripheral neuropathy may require brentuximab vedotin dose modifications, including a dose delay (see Section 5.2 Dose Modification Guidelines).

Infusion-related reactions, including anaphylaxis, have occurred with brentuximab vedotin.¹⁷ Monitoring of patients during infusion is required. If anaphylaxis occurs, the administration of brentuximab vedotin should be immediately and permanently discontinued and appropriate medical therapy administered. If an infusion-related reaction occurs, the infusion should be interrupted and appropriate medical management instituted. Patients who have experienced a prior infusion-related reaction should be premedicated according to institutional guidelines for subsequent infusions. Premedication may include acetaminophen, an antihistamine and a corticosteroid.

Clinically significant laboratory abnormalities were to be reported as adverse events per the phase 2 study protocols. The clinical laboratory parameters for which the most patients had new or worsening shifts to \geq Grade 3 were low neutrophils (11%), lymphocytes (11%), platelets (6%), leukocytes (5%), and high glucose (6%). Only 1 patient in the phase 2 studies had Grade 3 ALT and AST.

Any treatment that can decrease immune function may contribute to malignancy and infections; patients are to be monitored for these events during the treatment period and up to and including 30 days after the last dose of frontline therapy.

Complete blood counts should be monitored prior to each dose of brentuximab vedotin and more frequent monitoring should be considered for patients with Grade 3 or 4 neutropenia. Prolonged (\geq 1 week) severe neutropenia can occur. If Grade 3 or 4 neutropenia develops, manage by dose delays, reductions, or discontinuations (see Section 5.2 Dose Modification Guidelines).

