3.2 Secondary Endpoints

The key secondary endpoint is

AEs, SAEs, and assessments of clinical laboratory values

Other secondary endpoints include:

- PFS
- Duration of response
- CR rate
- The rate of interim PET-negativity
- OS

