6.2 Dose Modification Guidelines

Brentuximab vedotin dose modifications may change depending on the disease and combination with other drug(s).

Table 6-1 and Table 6-2 detail the recommended brentuximab vedotin dose modifications to be enacted in the event of treatment-associated toxicity.

Table 6-1 Recommended brentuximab vedotin Dose Modifications for Treatment-Associated Toxicity Excluding Neuropathy

Toxicity	≤Grade 2	Grade 3	Grade 4
Non-hematologic (excluding neuropathy)	Continue at same dose level.	Withhold dose until toxicity is ≤ Grade 1 or baseline, then resume treatment at the same dose and schedule ^a .	Withhold dose until toxicity is ≤ Grade 1 or has returned to baseline, then reduce dose to 1.2 mg/kg and resume treatment, or discontinue at the discretion of the investigator. ^a
Hematologic	Continue at same dose level.	Withhold dose until toxicity is ≤ Grade 2, or baseline, then resume treatment at the same dose level ^b . Consider growth factor support (G-CSF or GM-CSF) in subsequent cycles. ^b	Withhold dose until toxicity is ≤ Grade 2 or baseline, then resume treatment at the same dose and schedule. Consider growth factor support (G-CSF or GM-CSF) in subsequent cycles for patients who develop Grade 3 or Grade 4 neutropenia. ^b

NOTE: Grading based on National Cancer Institute (NCI) Common Terminology Criteria for Adverse Events (CTCAE) v. 4.03

- a Patients who develop Grade 3 or 4 electrolyte laboratory abnormalities may continue study treatment without interruption. Brentuximab vedotin will be held for clinically meaningful Grade 3 or 4 electrolyte abnormalities.
- b Patients who develop Grade 3 or 4 lymphopenia may continue study treatment without interruption.

Table 6-2 Dosing Recommendations for Treatment-Emergent or Worsening Peripheral Sensory or Motor Neuropathy

Severity of Peripheral Sensory or Motor Neuropathy (Signs and Symptoms [abbreviated description of CTCAE])	Modification of Dose and Schedule
Grade 1 (Asymptomatic; clinical or diagnostic observations only; intervention not indicated; paresthesia and/or loss of deep tendon reflexes)	Continue with the same dose and schedule
Grade 2 (Moderate symptoms; limiting instrumental activities of daily living)	Withhold dose until toxicity returns to \leq Grade 1 or baseline, then restart treatment at a reduced dose of 1.2 mg/kg every 3 weeks
Grade 3 (Severe symptoms; limiting self care activities of daily living)	

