8.1.2 Adverse Event Definition

Adverse event (AE) means any untoward medical occurrence in a patient or subject administered a pharmaceutical product; the untoward medical occurrence does not necessarily have a causal relationship with this treatment. An AE can therefore be any unfavorable and unintended sign (including an abnormal laboratory finding), symptom, or disease temporally associated with the use of a medicinal (investigational) product whether or not it is related to the medicinal product. This includes any newly occurring event, or a previous condition that has increased in severity or frequency since the administration of study drug.

An abnormal laboratory value will not be assessed as an AE unless that value leads to discontinuation or delay in treatment, dose modification, therapeutic intervention, or is considered by the investigator to be a clinically significant change from baseline.

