8.2 Procedures for Reporting Serious Adverse Events

AEs may be spontaneously reported by the patient and/or in response to an open question from study personnel or revealed by observation, physical examination, or other diagnostic procedures. Any clinically relevant deterioration in laboratory assessments or other clinical finding is considered an AE. When possible, signs and symptoms indicating a common underlying pathology should be noted as one comprehensive event. AEs which are serious must be reported to Millennium/Takeda Pharmacovigilance (or designee) from the first dose of brentuximab vedotin up to and including 30 days after administration of the last dose of brentuximab vedotin. Any SAE that occurs at any time after completion of brentuximab vedotin treatment or after the designated follow-up period that the sponsor-investigator and/or sub-investigator considers to be related to any study drug must be reported to Millennium/Takeda Pharmacovigilance (or designee). Planned hospital admissions or surgical procedures for an illness or disease that existed before the patient was enrolled in the trial are not to be considered AEs unless the condition deteriorated in an unexpected manner during the trial (e.g., surgery was performed earlier or later than planned). All SAEs should be monitored until they are resolved or are clearly determined to be due to a patient's stable or chronic condition or intercurrent illness(es).

Since this is an investigator-initiated study, the principal investigator, [name], also referred to as the sponsor-investigator, is responsible for reporting serious adverse events (SAEs) to any regulatory agency and to the sponsor- investigator's EC or IRB. Regardless of expectedness or causality, all SAEs must also be reported to Millennium/Takeda Pharmacovigilance (or designee) within 24 hours of the sponsor-investigator's observation or awareness of the event (contact information provided below).

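### Section 7.1.8 plans no graded table of laboratory values, so whether Grade 3-4 lymphopenia is counted by grade rests mainly on the investigator reporting it as an AE

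*Combined protocol and SAP*

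**What the plan says.** Section 3.2 defines the key secondary endpoint as "AEs, SAEs, and assessments of clinical laboratory values", and 2.2 states the matching objective as a safety profile by CTCAE 4.03.

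Section 7.1.8 assesses laboratory results "by changes from baseline in the patient's vital signs, weight, and clinical laboratory results using the safety population". Section 4.1 likewise pairs CTCAE evaluation with change from baseline. The only graded tabulations that 7.1.8 names are of adverse events, such as "Grade 3 or higher treatment-emergent AEs" and the drug-related subset. No table of laboratory values by worst grade or by grade shift is specified. For continuous variables, 7.1 sets the default summary as n, mean, SD, median, minimum and maximum.

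Whether a laboratory value reaches the AE tables is governed by two sections:

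- Section 8.1.2: "An abnormal laboratory value will not be assessed as an AE unless that value leads to discontinuation or delay in treatment", a dose change or an intervention, "or is considered by the investigator to be a clinically significant change from baseline".
- Section 8.2: "Any clinically relevant deterioration in laboratory assessments or other clinical finding is considered an AE".

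Table 6-1 note b adds: "Patients who develop Grade 3 or 4 lymphopenia may continue study treatment without interruption". Note a says the same of Grade 3-4 electrolyte abnormalities, but requires the drug to be held when they are clinically meaningful.

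**The concern.** The laboratory half of the key secondary endpoint is planned as a summary of averages, while the objective is framed in CTCAE grades. A mean change does not say how many patients reached Grade 3 or 4. The AE tables do give graded counts, but only for values that qualify as AEs. Lymphopenia is the parameter most likely to fall between the two, because note b removes the dosing response that would otherwise make it an AE.

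At stake is comparability with the protocol's own account of the drug. Section 1.6 describes laboratory risk as graded shifts. It introduces its figures with "The clinical laboratory parameters for which the most patients had new or worsening shifts to" Grade 3 or higher and gives lymphocytes 11%. The plan names no table that could be set beside that figure. Because this is a multi-center trial, the AE route also depends on judgement that may differ between sites.

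**Working it through.** **1. Which route counts a Grade 3-4 laboratory value by grade?**

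| Value | Dosing response in Table 6-1 | Route into a graded table |
|---|---|---|
| Neutrophils, platelets, leukocytes (Grade 3-4) | Dose withheld | The delay makes it an AE under 8.1.2 |
| Glucose (Grade 3-4, non-hematologic) | Dose withheld | Same |
| Electrolytes, clinically meaningful (Grade 3-4) | Dose held (note a) | Same; an intervention also qualifies |
| Electrolytes, other (Grade 3-4) | May continue | Intervention or investigator judgement |
| Lymphocytes (Grade 3-4) | May continue (note b) | Mainly investigator judgement |

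The gap is therefore narrow. It consists mainly of Grade 3-4 lymphopenia that is neither acted on nor judged clinically significant or relevant.

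**2. Do the planned continuous summaries close it?** No. The mean and SD give no count above a grade threshold, and the minimum shows one extreme value, not the number of patients beyond a limit.

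**3. How many patients might be involved?**

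Inputs:
- N = 25, from 7.1.1. This reproduces: 22/(1 - 0.10) = 24.4, rounded up to 25. The underlying 2/10, 7/22 design also reproduces as the optimal Simon design, with exact alpha 0.0492 and power 0.806.
- p = 0.11, the rate of new or worsening lymphocyte shifts to Grade 3 or higher in 1.6. It comes from Hodgkin lymphoma and sALCL patients, so applying it here is an assumption. A range of 6% to 20% is also assumed.

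Formulas: expected number = N × p; P(at least one) = 1 - (1 - p)^N.

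| Assumed rate | Expected among 25 | P(at least one) |
|---|---|---|
| 6% | 25 × 0.06 = 1.5 | 1 - 0.94^25 = 0.787 |
| 11% | 25 × 0.11 = 2.75 | 1 - 0.89^25 = 0.946 |
| 20% | 25 × 0.20 = 5.0 | 1 - 0.80^25 = 0.996 |

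At 11% the chance of at least two such patients is 0.778, and of at least three 0.529. With 22 patients instead of 25, the expected number is 22 × 0.11 = 2.42 and the chance of at least one is 0.923.

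These figures count patients who would shift to Grade 3 or higher lymphopenia. They do not count patients missed by the AE tables; that number depends on investigator judgement, for which the documents give no rate.

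**The case against.** The strongest reply is that the plan already captures what matters. Section 8.1.2 admits any change that the investigator considers clinically significant, with no action needed. Section 8.2 admits any clinically relevant deterioration. Section 7.1.4 has all available safety data listed and tabulated, and 7.1 provides number and percent for categorical data. A grade shift is itself a form of change from baseline, so its layout might be left to table shells in a 25-patient single-arm study.

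Much of this stands, and it rules out several stronger readings:

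- A reader might infer that severe laboratory abnormalities would go unreported. Section 7.1.4 contradicts this; what is missing is a graded count, not the data.
- A reader might infer that every value not acted on is kept out of the AE tables. The judgement route in 8.1.2 and 8.2 contradicts this.
- A reader might give electrolytes equal weight. They are a minor case, because clinically meaningful Grade 3-4 abnormalities lead to a hold and so qualify as AEs. The documents give no electrolyte rate.
- A reader might infer that AE tables always undercount laboratory toxicity. In the pivotal studies, Grade 3 or higher neutropenia was 20% as an AE (1.4) against 11% as a laboratory shift (1.6). The two sources differ, but here the AE figure is the higher.
- A reader might infer that pre-dose values are largely selected after recovery. The sample that triggers a hold can itself be the pre-dose sample, and lymphopenia carries no hold.

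The reply does not supply the missing summary. A listing gives no incidence, 7.1.4 specifies no grading, and 7.1.8 names no categorical laboratory table.

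**Conclusion.** The point holds in a limited form. Section 7.1.8 specifies change from baseline for laboratory values and graded tables for AEs only. Grade 3-4 lymphopenia could therefore appear in the listings yet be counted in no graded table, depending mainly on investigator judgement under two differently worded thresholds.

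If the 11% from 1.6 carried over, about 2.75 of 25 patients would have such a shift, and at least one would be almost certain to occur (0.95). Over assumed rates of 6% to 20%, 1.5 to 5.0 patients would be expected. How many of them would escape the AE tables cannot be estimated from the documents.

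A reader might go further and tie the gap to detection of PML. The protocol says that PML typically occurs in immunocompromised individuals but draws no link to lymphocyte counts, so the finding does not rest on that. The primary endpoint, sample size and error rates are unaffected. This is a worthwhile, inexpensive improvement to the safety analysis.

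**What to change.** In 7.1.8, for each hematology and chemistry parameter that is collected and gradable by CTCAE 4.03:

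1. Tabulate baseline grade against worst post-baseline grade through 30 days after the last dose, in the safety population.
2. Use all scheduled and unscheduled values, whether or not they were reported as AEs.
3. Report the number and percent of patients with a new or worsening shift to Grade 3 or higher.
4. Keep change from baseline as a supplement.

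Separately, reconcile the AE threshold for laboratory values between 8.1.2 (clinically significant in the investigator's view) and 8.2 (clinically relevant), so that sites apply one rule.

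The cost is a paragraph of analysis text and a small amount of programming. Hematology and chemistry are already drawn at screening, before each dose and at end of treatment. Footnote f to the schedule does not list the individual analytes, so confirm that lymphocyte counts and electrolytes are recorded; the table covers only what is collected. No change to any dosing rule is implied.
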